In pursuit of our long-term goal, our team has recently developed a framework for prosthetic socket design and fabrication [26] that involves: 1) non-invasive imaging to record patient geometry, 2) indentation to assess tissue mechanical properties, 3) data-driven and automated creation of patient-specific designs, 4) patient-specific finite element analysis (FEA) and design evaluation, and 5) 3D printing of the end design for clinical evaluation.

II. OBJECTIVES

The overall goal of this study is to further develop and clinically assess a computational and data-driven design and manufacturing framework for mechanical interfaces that quantitatively produces transtibial prosthetic sockets in a faster and more cost-effective way than conventional processes. Traditionally, prosthetic socket production has been a craft activity, based primarily on the experience of the prosthetist. Even with advances in computer-aided design and computer-aided manufacturing (CAD/CAM), the design process remains manual. The manual nature of the process means it is non-repeatable and currently largely non-data-driven, and quantitative data is either not obtained or insufficiently employed. Furthermore, discomfort, skin problems and pressure ulcer formation remain prevalent. Through the proposed computational modeling framework, a repeatable, data-driven and patient-specific design process is made available which is based on scientific rationale.

Objective/hypothesis: The main hypothesis of this proposal is that a socket, designed using the novel computational design framework, is equivalent to, or better than, a conventional socket (designed by a prosthetist) in terms of: 1) skin contact pressures, 2) gait symmetry, 3) walking metabolic cost, 4) skin irritation levels as assessed by the dermatologist, and 5) comfort as evaluated from a questionnaire. Our hypothesis is supported by the presented pilot data which shows reduced or equivalent skin contact pressures and subject reported comfort levels for several critical anatomical regions.

Specific Aims: 1) Subject-specific biomechanical modeling for N=18 subjects, 2) Computational design and fabrication of sockets for N=18 subjects, and 3) Clinical evaluation of novel sockets for N=18 subjects.

III. STUDY POPULATION

Sample Size

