A total of 18 subjects will be recruited for this study. The worst ratio between the mean and standard deviation for pilot contact pressure measurements for static standing was observed for the mid posterior wall, which presented with a mean of 97 kPa, and standard deviation of 8.9 kPa. If two-tailed t-test based analysis is assumed, aiming to detect at least a 10% difference with respect to this mean, with a significance level of 0.05 and a power of 90%, the theoretically required number of test subjects is 12 (power analysis based on the MATLAB *sampsizepwr* function). However, to increase the chances of significant statistics for all measures (with varying signal to noise ratios), while also anticipating potential candidate drop-out, inclusion of N=18 subjects is proposed here.

Statistical analysis of the socket clinical evaluation data will focus on the following measurements: 1) local skin contact pressures, 2) metabolic power, 3) gait parameters (symmetry indices for joint angles, positions, torques, and also ground reaction forces), and 4) the socket evaluation questionnaire. For scalar comparisons a paired t-test, with the level of significance set at 0.05, will be used to test for differences between the novel and conventional sockets. For time-series analysis of variance (ANOVA) will be used.

Inclusion and exclusion criteria

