In pursuit of our long-term goal, our team has recently developed a framework for prosthetic socket design and fabrication that involves: 1) non-invasive imaging to record patient geometry, 2) indentation to assess tissue mechanical properties, 3) data-driven and automated creation of patient-specific designs, 4) patient-specific finite element analysis and design evaluation, and 5) 3D printing of the end design for clinical evaluation. This study aims to advance these approaches, and clinically assess the overall design process for N=18 transtibial amputees. Socket evaluations are conducted during standing and walking activities. For these evaluations, skin-socket interface pressures are recorded using sensors located at the skin-socket interface. During the walking evaluation, motion capture is used additionally to allow for gait analysis. Furthermore, metabolic cost is measured by indirect calorimetry using an open circuit respirometry system. These experiments are repeated for each patient's conventional socket for comparison. In addition to these quantitative evaluations, each study participant completes a socket evaluation questionnaire, and a certified dermatologist writes a report documenting skin conditions subsequent to each socket test.

The main hypothesis of this proposal is that the novel quantitative socket is equivalent to, or better than, a conventional socket in terms of: 1) skin contact pressures, 2) gait symmetry, 3) walking metabolic cost, 4) skin irritation levels as assessed by the dermatologist, and 5) comfort as evaluated from a questionnaire. Furthermore, we hypothesize that equivalence or improved socket performance can be achieved for all N=18 subjects using a single computational design framework, i.e. that we can formulate the computational design framework such that it can automatically design these sockets for all subjects without requiring algorithm adjustments from one subject to the next.

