In order to address the hypothesis that the novel sockets can perform equivalently to, or better than, conventional sockets (designed by a qualified prosthetist) we propose an experimental evaluation using N=18 subjects. Static standing and walking exercises will be performed. During the standing and walking exercise skin contact pressures will be recorded. During walking skin contact pressure, metabolic cost, and motion capture data will be recorded. Finally, a custom socket evaluation questionnaire will be used to assess the level of socket comfort experienced by the subject.

This study consists of three phases:

- 1) Data collection
- 2) Socket design
- 3) Socket evaluation

Participant involvement is required for phase 1 and 3 which occur in two separate sessions.

Session 1 (phase 1): Data collection

In the first session, each amputee participant will be scheduled to visit the Biomechatronics Group in The MIT Media Laboratory and our imaging center (the MIT McGovern Institute). The main purpose of this session is to quantitatively measure the stiffness of the residual limb and map out the anatomy of the residual limb, for N=18 subjects, by using Magnetic Resonance Imaging (MRI), 3D scanner, ultrasound scanner, and a stiffness-measuring device on the amputee. Mechanical property investigation may also take place during imaging, e.g. during MRI by using MRI compatible indenter systems. Subjects are scanned using a 3T MRI system (Siemens Magnetom 3 Tesla, Siemens Medical Systems, Erlangen, Germany). The structural and geometrical data derived from MRI (e.g. using segmentation) provides the input for computational model development (used in the socket design process). Morphological data (such as height, weight, limb length and circumference) of the participant will also be recorded.

Session 2 (phase 3): Socket evaluation.

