# Statistical analysis plan

Statistical analysis of the socket clinical evaluation data will focus on the following measurements:

1. local skin contact pressures
2. metabolic power
3. gait parameters (symmetry indices for joint angles, positions, torques, and ground reaction forces)
4. the socket evaluation questionnaire

For scalar comparisons a paired t-test, with the level of significance set at 0.05, will be used to test for differences between the novel and conventional sockets. For time-series analysis of variance (ANOVA) will be used.

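### The main hypothesis is equivalence or improvement, but the plan has only difference tests and no margin, so it cannot support the equivalence half

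*SAP*

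**What the plan says.** Protocol II (Objectives) gives as the main hypothesis that the novel socket "is equivalent to, or better than, a conventional socket (designed by a prosthetist) in terms of" skin contact pressure, gait symmetry, metabolic cost of walking, skin irritation and comfort. Protocol V (Methods) repeats this and says the evaluation in 18 subjects is there to address "the hypothesis that the novel sockets can perform equivalently to, or better than, conventional sockets".

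The SAP's statistical section, in the same words as Protocol III (Sample Size), says that for scalar outcomes "a paired t-test, with the level of significance set at 0.05, will be used to test for differences between the novel and conventional sockets". It adds: "For time-series analysis of variance (ANOVA) will be used".

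The sample size in Protocol III also rests on a difference test: a two-tailed t-test "aiming to detect at least a 10% difference with respect to this mean, with a significance level of 0.05 and a power of 90" per cent. This gives 12 subjects. The number is raised to 18 partly for drop-out and partly "to increase the chances of significant statistics for all measures (with varying signal to noise ratios").

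Protocol V adds a second hypothesis, that "equivalence or improved socket performance can be achieved for all N=18 subjects using a single computational design framework". It explains this as meaning that "it can automatically design these sockets for all subjects without requiring algorithm adjustments from one subject to the next".

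**The concern.** A difference test can reject equality. If it does so in the favourable direction, that supports better. If it does not reject, nothing has been shown: p>0.05 is compatible with no difference and with a harmful difference measured imprecisely. The plan therefore gives the equivalence half of its hypothesis no decision rule. No passage says that p>0.05 will be read as equivalence. The defect is that no valid rule is offered in its place.

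That half matters. Protocol III admits only subjects whose conventional socket is already judged comfortable and of high quality, so matching it is a likely result, and the plan has no way to declare it. If p>0.05 were used informally instead, the error rate of an equivalence statement would rise with the noise of the outcome, and the protocol itself expects noise to vary between outcomes. The gap also works in reverse: a small unfavourable difference can be significant, with no rule to say whether it is acceptable.

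A test of the group mean also says nothing about whether every subject did as well or better.

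**Working it through.** **Inputs.** From Protocol III (Sample Size): mean 97 kPa, SD 8.9 kPa (static standing, mid posterior wall), difference to detect 10% = 9.7 kPa, two-sided α 0.05, power 90%, calculated N 12, planned N 18. The protocol does not say whether 8.9 kPa is the SD of paired differences. Three SDs of differences are therefore used:

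- 8.9, taken at face value;
- 12.6 = 8.9 × √2, if 8.9 is a single-socket SD and the two sockets are uncorrelated (assumption);
- 17.8 = 2 × 8.9, to illustrate a noisier outcome (assumption).

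The documents give no margin. The 10% (9.7 kPa) and 5% (4.85 kPa) margins below are illustrations.

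**1. The plan's own figure.** For a paired t-test the noncentrality is 9.7 × √n / 8.9. At n=11 it is 3.615 and power is 90.2%; at n=12 it is 3.775 and power is 92.9%. The smallest n is 11, close to the stated 12. The figure is sound for detecting a difference.

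**2. Chance of p>0.05 when the novel socket is truly 10% worse.** P = F(t_c) − F(−t_c), where F is the noncentral t distribution function with n−1 degrees of freedom and noncentrality 9.7 × √n / SD, and t_c is the 97.5% point of t (2.110 at n=18, 2.201 at n=12).

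| SD of differences (kPa) | N=18 | N=12 |
|---|---|---|
| 8.9 | 0.8% | 7% |
| 12.6 | 13% | 32% |
| 17.8 | 41% | 59% |

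Under a confidence-interval rule with a 10% margin, the chance of wrongly concluding equivalent or better at this true difference would be 2.5% whatever the SD.

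**3. What N=18 offers under such a rule.** Non-inferiority power, one-sided 0.025, true difference zero: 1 − F(t_c), with noncentrality margin × √n / SD.

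| SD (kPa) | 10% margin, N=18 | 10% margin, N=12 | 5% margin, N=18 | N for 90% power, 10% margin | N for 90% power, 5% margin |
|---|---|---|---|---|---|
| 8.9 | 99% | 93% | 59% | 11 | 38 |
| 12.6 | 87% | 68% | 34% | 20 | 73 |
| 17.8 | 59% | 41% | 19% | 38 | 144 |

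Eighteen subjects give 90% power only if the SD of differences is at most 12.0 kPa (10% margin) or 6.0 kPa (5% margin).

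**4. The reverse gap.** At N=18 and SD 8.9 the 95% interval half-width is 2.110 × 8.9 / √18 = 4.43 kPa, or 4.6% of 97. Any larger unfavourable observed difference would be significant, and the plan does not say whether it would be acceptable.

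**5. The all-subjects hypothesis.** If all 18 subjects were within a margin, the exact 95% lower limit for the proportion is 0.025^(1/18) = 81.5%. For 16 of 18 the exact interval is 65.3% to 98.6%.

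**The case against.** The strongest reply is that the protocol's own figures show little harm. At SD 8.9 and N=18 a socket that is truly 10% worse escapes detection only 0.8% of the time. Moreover, if the observed SD of differences is 8.9, a result with p>0.05 must lie within 4.43 kPa of zero, so its 95% interval lies within 2 × 4.43 = 8.9 kPa, inside 9.7. This is correct, and holds at N=18 for an observed SD up to 9.7 / (2 × 2.110 / √18) = 9.75 kPa. It fails at N=12, where twice the half-width is 11.3 kPa. It also needs 10% to be accepted as a margin and 8.9 to be the SD of differences, and the protocol states neither. It covers one pressure site in static standing. The protocol calls that site the worst of the pilot standing-pressure sites, but gives no SD for walking pressure, gait, metabolic cost or the questionnaire.

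It is also fair that the SDs of 12.6 and 17.8 are assumed, so the larger percentages describe no documented outcome. They show how the risk moves with noise. The mismatch between hypothesis and test does not depend on them.

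The sample size is not in itself wrong: at a 10% margin and SD 8.9, non-inferiority needs 11, the same as the difference test. The all-subjects hypothesis can be read mainly as an engineering claim about a single algorithm, so that part carries less weight.

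Finally, setting margins is real work. Four sites in standing and walking (8), three joints by angle, position and torque (9), vertical ground reaction force (1), metabolic cost (1) and at least one questionnaire score (1) make at least 20 outcomes.

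**Conclusion.** The concern holds. In the text available (part of the SAP file could not be examined), the main hypothesis is equivalence or improvement, while every planned analysis is a difference test with no margin, interval rule or definition of equivalence. Followed exactly, the plan can support better for an outcome but never equivalent. This needs to be fixed before the first evaluation session, because a margin chosen after seeing results is not credible.

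The practical size is uncertain. For mid posterior wall pressure in standing, the risk of missing a true 10% worsening is 0.8% at N=18 if 8.9 kPa is the SD of paired differences. It rises to 13% or 41% under the two assumed larger SDs, and further with drop-out. For the other outcomes the documents give no figures from which to judge.

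**What to change.** Amend Protocol III (Sample Size) and the SAP's statistical section as follows.

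- For each scalar outcome, report the paired difference (novel minus conventional) with a two-sided 95% confidence interval, and state which direction is unfavourable.
- Conclude equivalent or better only if the unfavourable limit lies within a margin justified and fixed before the first evaluation session. Then test superiority from the same interval. If the interval includes the margin, report the outcome as inconclusive.
- State that p>0.05 is not evidence of equivalence.
- Use the 10% from the sample-size paragraph as a contact-pressure margin only if the sponsor can justify it as acceptable. At present it is a difference to detect at one site.
- For gait, base any equivalence claim on scalar symmetry indices; the ANOVA can support only a difference.
- Skin irritation is one of the five domains but is missing from the list of analysed measurements, and it is recorded as a report with no numeric scale. Either pre-specify a grade or describe it outside this rule.
- State whether the overall claim needs every outcome to meet its margin or is made outcome by outcome.
- For the all-subjects hypothesis, report descriptively how many subjects fall within the margin, with an exact 95% interval, noting that measurement noise affects the count.

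If margins cannot be justified for some outcomes, the honest alternative is to restate the hypothesis for those as one of difference or superiority.

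The cost is wording and the justification of margins. The paired data are unchanged, and a graded skin score is needed only if that domain comes under the rule. The price is commitment: some outcomes may be inconclusive at N=18, where power is 59% with a 10% margin and SD 17.8, or with a 5% margin and SD 8.9.
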